13.1. Efficacy Analysis

13.1.1. Analysis Populations

The following subject populations will be evaluated and used for presentation and analysis of the data:

- The Intent-to-Treat (ITT) Population will include all randomized subjects who receive any amount of investigational product (OCA or placebo). The ITT Population will be the primary population used for efficacy analyses. Treatment assignment will be based on the randomized treatment.
- The Per Protocol (PP) Population will include all ITT subjects who do not have any major protocol violations that potentially affect the efficacy conclusion. Treatment assignment will be based on the randomized treatment.
- The Safety Population will include all subjects who received any amount of investigational product (placebo or OCA). The Safety Population will be the primary population used for safety analyses. Treatment assignment will be based on the treatment actually received.
- The PK Population will include all OCA subjects who have at least one confirmed fasted analyzable sample. Subjects must have been fasting for approximately 8 hours prior to the visit and must not have any major protocol deviations that potentially affect exposure levels. The PK population will be used for OCA PK analyses.
- The Overall Historical Control Population will include subjects from the United Kingdom (UK) -PBC Group and Global PBC Study Group databases with demonstrated comparability to randomized subjects in this clinical study (747-302) with respect to both subject characteristics and disease progression.
- The UK-PBC Historical Control Population will include subjects from the UK-PBC Group databases with demonstrated comparability to randomized subjects in this clinical study (747-302) with respect to both subject characteristics and disease progression.

- The Global PBC Historical Control Population will include subjects from the Global PBC Study Group database with demonstrated comparability to randomized subjects in this clinical study (747-302) with respect to both subject characteristics and disease progression.

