13.1.3. Primary Efficacy Analysis

The primary efficacy endpoint will be the time to first occurrence of one of the following post-randomization:

- Death (all-cause)
- Liver transplant
- MELD score ≥ 15
- Hospitalization (as defined by a stay of 24 hours or greater) for new onset or recurrence of:
 - Variceal bleed
 - Hepatic encephalopathy (as defined by a West Haven score of ≥ 2)
 - Spontaneous bacterial peritonitis (confirmed by diagnostic paracentesis)
- Uncontrolled ascites (diuretic resistant ascites requiring therapeutic paracentesis at a frequency of at least twice in a month).

The primary efficacy analysis will compare OCA to placebo with respect to the primary efficacy endpoint using the ITT population. Only adjudicated events will be included in analyses. The 2 treatment groups will be compared using the log rank test stratified by the randomization stratification factor. Kaplan-Meier (KM) estimates of the distribution of the time-to-event will be tabulated and graphed by treatment group. The tabulation will include the KM estimate of the medians and corresponding 95% confidence intervals (CIs), if the medians can be estimated. The number and percent of subjects censored and with events will be presented. The hazard ratio and 95% CI will be determined based on a Cox regression model stratified by randomization strata to estimate the magnitude of the effect. The same analyses for primary efficacy endpoints will be performed for PP population as a sensitivity analysis.

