13.1.9. Handling of Dropouts or Missing Data

Subjects who discontinue investigational product are expected to continue in the study until study termination.

Missing data will be assumed to be missing at random. In order to determine the effect of missing data on the analysis, efficacy endpoints will be analyzed using different methods of imputation as described below. In addition, the same analyses for primary and key secondary endpoints based on ITT and PP populations will be performed to assess robustness of analysis results. During the conduct of the study, the DMC may recommend refining the missing data strategy to better address the observed pattern of missing data, based on blinded monitoring of the data.

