13.1.9.1. Time to Event Endpoints

For the time to event analyses, subjects who do not experience an event will be censored at the time of their last contact. Subjects with no data after randomization will be considered to have an event on Day 1 (first day of investigational product dosing).

For analyses of the percentage of subjects with an event, subjects with no data after randomization will be considered to have an event.

All time to event endpoints include only adjudicated events. Sensitivity analyses may consider all events regardless of adjudication. Events with discrepant adjudication will be analyzed using both results.

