13.4. Adjudication Committees

All suspected liver-related clinical outcomes, MACE/Expanded MACE, and drug-related hepatic injury events that occur after administration of the first dose of investigational product will be reviewed by the following blinded adjudication committees, depending on event type, before inclusion in any analysis. The 3 committees and event types they are responsible for adjudicating are as follows:

- Cardiovascular Adjudication Committee (CAC): Adjudicates all suspected MACE, including all deaths
- Hepatic Outcomes Committee: Adjudicates all deaths and suspected liver-related outcomes
- Hepatic Safety Committee: Adjudicates all suspected drug-related hepatic injury events

Each adjudication committee will have a charter that documents the reporting of events by the study site, definition of the suspected events to be adjudicated, supply of source documentation to the committee, entire data flow and process from committee membership, review of the events by the committee, reporting of the final assessment, and the working procedures of the committee.

The adjudication committee members will include experts with relevant adjudication experience; they will not be involved in the study as Investigators, DMC members, or consultants. Any candidate found to have a conflict or whose name is listed on the FDA debarment list is not offered membership. Conflicts of interest are assessed regularly, and if members are found to have a new conflict of interest they will be replaced.

The adjudication of suspected events will be based on available source documentation, including but not limited to individual clinical study data, hospital records, histology, discharge summaries, and/or death certificates. The adjudication committees will not receive any individual subject treatment or site-specific information. The assessment of events will be conducted in compliance with study-specific procedures, manuals, good clinical practice (GCP), and all other applicable regulatory requirements, including the archiving of essential documents.

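### Subjects with no data after randomisation are scored as Day 1 events in the time-to-event analyses, against the protocol's own adjudicated-events-only rule; few subjects are likely to be affected

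*Protocol*

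**What the plan says.** Section 13.1.9.1 sets two rules for time-to-event analyses. In general, "subjects who do not experience an event will be censored at the time of their last contact". The exception is: "Subjects with no data after randomization will be considered to have an event on Day 1 (first day of investigational product dosing". A parallel sentence treats the same subjects as having an event when percentages of subjects with an event are analysed. Neither sentence is limited to sensitivity analyses.

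The section then says: "All time to event endpoints include only adjudicated events". It mentions unadjudicated events only as something that sensitivity analyses may consider. Section 13.1.3 says of the primary analysis that "Only adjudicated events will be included in analyses", and Section 13.1.4 repeats the restriction for the key secondary time-to-event endpoints. Section 13.4 gives the basis: "The adjudication of suspected events will be based on available source documentation". The general assumption in Section 13.1.9 is: "Missing data will be assumed to be missing at random".

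On the population, Section 13.1.1 reads: "The Intent-to-Treat (ITT) Population will include all randomized subjects who receive any amount of investigational product (OCA or placebo". Sections 9.1 and 9.7.7 place the first dose on the day after the randomisation visit.

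**The concern.** Both rules cannot be followed for the same subject. An event assigned because data are absent has no source documents, so a committee cannot confirm it. Yet it would enter the primary test: "The 2 treatment groups will be compared using the log rank test stratified by the randomization stratification factor".

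The imputed value is also implausible. Section 8.3 excludes subjects with a current MELD score above 12 or recent decompensation, so silence after randomisation is poor evidence of death, transplant or end-stage disease on the first dosing day. Because the rule is not tied to one endpoint, the same subject fails on Day 1 for MELD of 15 or more and for transplant or death, which are steps 2 and 3 of the hierarchy in Section 13.1.10. Those endpoints are built from components of the composite and cannot have more events than it has, so one imputed event weighs at least as much there. The percentage rule would likewise count a no-data subject as progressing to cirrhosis in the Section 13.1.5 comparison.

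With 127 planned events, a small number of artificial ones can shift the estimate, and the direction depends on the arm in which they fall.

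**Working it through.** **Inputs (Sections 13.1.2 and 13.1.12).** Hazard ratio 0.60, 1:1 allocation, two-sided 5%, 127 events for 80% power, about 428 subjects, 10% dropout, placebo survival 0.6 at 8 years, 4 years of accrual plus 6 of follow-up, Lan-DeMets O'Brien-Fleming looks at 64 and 96 events. The number of subjects with no data after randomisation is not given; every count below is an assumption.

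**The plan's own figures reproduce.**
- Fixed design: 4 × (1.96 + 0.8416)² / (ln 0.6)² = 120.3, so 121 events.
- With the two interim looks, 127 events give 79.7% power (Freedman drift) or 81.3% (Schoenfeld drift).
- Mean event probability is 0.3308; 127 / 0.3308 = 384, and 384 / 0.9 = 427, against 428 stated.

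**Score approximation.** With 1:1 allocation, V = 127/4 = 31.75. At a hazard ratio of 0.60, U = 0.5108 × 31.75 = 16.22. On Day 1 almost everyone is still at risk, so each imputed event adds 0.5 to observed minus expected in its own arm and 0.25 to V. The implied hazard ratio is exp(−U/V), and power at the final boundary of 2.016 is Φ(U/√V − 2.016).

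| Assumed no-data subjects | U | V | Hazard ratio | U/√V | Power |
|---|---|---|---|---|---|
| None | 16.22 | 31.75 | 0.60 | 2.878 | 81% |
| 4 OCA, 4 placebo | 16.22 | 33.75 | 0.62 | 2.792 | 78% |
| 6 OCA, 2 placebo | 14.22 | 33.75 | 0.66 | 2.448 | 67% |

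A one-subject imbalance moves z by 0.5/√31.75 = 0.09.

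**No true effect.** With none imputed, the one-sided error at 2.016 is 2.2%. With 2 on OCA and 6 on placebo, the score shifts by 2 in favour of OCA: 2/√33.75 = 0.344, and 1 − Φ(2.016 − 0.344) = 4.7%.

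**Arm-independent loss.** Each imputed event then contributes +0.5 or −0.5 at random, with variance 0.25. That is exactly what it adds to V, so the overall error rate is unchanged.

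**Simulation check.** Unstratified two-arm log-rank, final analysis only at 1.96, 214 per arm, 10% dropout spread over 8 years (an assumption), imputed events on top of 127 real ones:
- None imputed: hazard ratio 0.60, power 82%.
- 4 per arm: 0.62, 80%.
- 4 on OCA only: 0.65, 69%.
- 4 on placebo only: 0.57, 89%.
- No true effect: 4 on placebo only gives a one-sided error of 5.5% (4.3% if the imputed events count within the 127); 4 per arm gives 2.2% to 2.4%.
- The same kinds of split censored at Day 1 instead (4 per arm, 8 per arm, 8 in one arm only): hazard ratio 0.60, power 81% to 83%.

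**The case against.** The strongest objection is reach. ITT membership needs receipt of product, and the first dose is taken at home the day after randomisation. Evidence of dosing comes later, from tablet counts and diaries (Section 9.3) or the Month 1 contact (Section 9.7.8). A subject with no later data will usually have no evidence of dosing and so fall outside the primary population. This largely stands. It is not complete, because Section 13.1.1 does not say whether product dispensed at the Day 0 visit counts as received. If it does, a subject who takes a bottle and never returns is caught.

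Two further defences are partial. Counting no-data subjects as failures matches the non-responder rule in Section 13.1.9.3, and Section 13.1.9 promises alternative imputations and lets the DMC suggest refinements. Neither says which of the two conflicting rules governs the primary test.

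A reader might infer more than the documents support:
- That the type I error is inflated. This needs loss concentrated on placebo before any contact in a double-blind trial, and nothing in the protocol suggests that. Section 5.6 names pruritus as the main OCA-related adverse event, so any tolerability loss would more plausibly fall on OCA and count against it.
- That the 10% dropout, about 43 of 428, becomes Day 1 events. Dropout is not absence of all data; subjects with any later contact and no event are censored at that contact.
- That imputed events use up the 127. Sections 7.1, 7.2, 7.5 and 13.1.2.1 specify adjudicated events for that target. The looks at 64 and 96 in Section 13.1.12 are worded less tightly.
- That the ITT definition must change to cure this. That is a separate question: an undosed subject with no data, censored at Day 0, adds nothing to the log-rank test, just as if excluded.

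**Conclusion.** The rule is wrong as written, with modest severity. Section 13.1.9.1 puts events that cannot be adjudicated into analyses restricted to adjudicated events, and it replaces a missing-at-random assumption with certain failure on Day 1 for one group of subjects. This is a contradiction between stated rules, not a detail left to the SAP.

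Its practical effect is probably small and cannot be sized from the protocol. The figures above show sensitivity to assumed counts and are not predictions: a small dilution for balanced loss, a material loss of power for an OCA-heavy split, and excess one-sided error only for a placebo-heavy split. They rest on a score approximation and an unstratified simulation, with each split held fixed.

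**What to change.** In Section 13.1.9.1:
1. Censor subjects with no post-randomisation data at randomisation (Day 0/Day 1) in the primary and all other time-to-event analyses.
2. Drop the matching rule for percentages of subjects with an event.
3. Keep the Day 1 event only as a labelled sensitivity analysis.
4. State that imputed events never count towards the 64, 96 and 127 adjudicated events.

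The SAP should carry the same wording, settled before the first interim analysis, which is the deadline that Section 13 sets for the SAP. The cost is protocol and SAP text; no data collection or sample size changes.

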13.1.9.2. Quantitative Endpoints

For efficacy endpoints that utilize an ANCOVA model, observed cases will serve as the primary analysis. Sensitivity analyses to assess the effect of missing data may be conducted where missing data is imputed using last observation carried forward.

Sensitivity analyses of ANCOVA models will also be evaluated using a restricted maximum likelihood based mixed-effect repeated measures model where no imputations will be made for missing values.

13.1.9.3. Responder Endpoints

In an efficacy analysis in which subjects are classified as either a responder or a non-responder (binary outcome) based on dichotomizing a continuous variable, any subject who does not provide an assessment at the specified time point for the defining of response will be considered to be a non-responder. That is, for the percentage of responders, the subject will be included in the denominator and will not contribute to the numerator.

For sensitivity analyses using only “observed cases,” subjects who do not provide an assessment at the specified timepoint for the defining of response will not be included. That is, for the percentage of responders, the subject will not be included in the numerator or the denominator.

13.1.10. Multiple Comparisons/Multiplicity

The key secondary efficacy endpoints are as follows:

- Time to MELD score ≥ 15
- Time to first occurrence of liver transplant or death (all-cause)
- Change from Baseline in total bilirubin at end of study
- Change from Baseline in ALP at end of study

The hypothesis testing of key secondary analyses will compare placebo and OCA and will be conducted in a sequential closed testing gate-keeping procedure (in the order in which the key secondary endpoints are stated above), provided that the primary efficacy endpoint comparison is statistically significant in favor of OCA. If the primary comparison is not statistically significant then comparison of the secondary endpoints will be considered as descriptive and exploratory. This procedure controls the study-wise type I error.

- First (step 1) placebo and OCA will be compared with respect to the primary efficacy endpoint. If the comparison achieves statistical significance at 2-sided 0.05 level in favor of OCA group, then
- The time to MELD score ≥ 15 will be compared between placebo and OCA (step 2). If the comparison achieves statistical significance at 2-sided 0.05 level in favor of OCA group, then
- The time to liver transplant or death (all-cause) will be compared between placebo and OCA (step 3). If the comparison achieves statistical significance at 2-sided 0.05 level in favor of OCA group, then
- Change from Baseline in total bilirubin will be compared between placebo and OCA (step 4). If the comparison achieves statistical significance at 2-sided 0.05 level in favor of OCA group, then
- Change from Baseline in ALP at the end of study will be compared between placebo and OCA (step 5).

If at any step defined above the comparison is not statistically significant at the 2-sided 0.05 level then the remaining comparisons in the stated hierarchy will be considered descriptive

and exploratory. The study-wise type I error will be maintained with the above closed procedure.

Additional efficacy endpoints will be analyzed; however, hypothesis tests will be applied for descriptive and exploratory purposes only.

13.1.11. Examination of Subgroups

The primary and secondary efficacy endpoints will be analyzed for subject subgroups based on the ITT population. Subgroups will be assessed at Baseline and only if there are a sufficient number of subjects in each group (eg, >5 subjects per group).

Baseline subgroups of interest are as follows: age, age at PBC diagnosis, sex, race, body mass index, ALP level, bilirubin level, use of UDCA, years since diagnosis of PBC, and geographic region.

The primary efficacy endpoint will also be assessed across the spectrum of PBC disease stage as defined by Rotterdam criteria ([Kuiper 2009](#))

- Early (normal albumin and normal bilirubin)
- Moderate (abnormal albumin or abnormal bilirubin)
- Advanced (abnormal albumin and abnormal bilirubin)

The primary efficacy endpoint will also be assessed for the following clinically relevant subpopulations.

- Monotherapy in patients who are intolerant or non-responsive to UDCA
- Elderly patients

Assuming a strong correlation between biochemistry and clinical outcomes using the total study population ([Section 13.1.5.1](#)) is observed, we will further assess the biochemical improvement in relevant subpopulations as applicable (eg, Rotterdam disease severity and monotherapy) and estimate the reduction in risk of clinical outcomes associated with the biochemical improvement.

Additional details regarding statistical methods and subgroup definitions will be provided in the SAP.

13.1.12. Continuous Monitoring and Interim Analyses

Blinded safety reports including the accrual of events, drop outs, and/or loss of subjects to commercially available OCA will be reviewed by the DMC on a regular basis.

Two planned interim analyses of the liver-related outcomes will be conducted using the Lan-DeMets O'Brien-Fleming boundaries ([Reboussin 2000](#)). Both interim analyses will be pre-specified and will occur after accrual of 50% (64 events) and 75% (96 events) of clinical outcome events, respectively.

The DMC will review the available efficacy data in conjunction with detailed safety data and other relevant information to recommend continuation, modification, or cessation (for efficacy) of the study beyond each interim analysis. Modification of the study would not take place without prior agreement with regulatory authorities.

13.2. Safety Analysis

Safety data, including AEs and clinical laboratory observations, will be summarized by treatment group using the Safety Population.

13.2.1. Adverse Events

AEs will be coded using the Medical Dictionary of Regulatory Activities. Summary tables of treatment-emergent AEs will be provided. The incidence of TEAEs will be tabulated by system organ class and preferred term for each treatment group, and by severity and relationship to treatment. Tables of TEAEs leading to investigational product discontinuation and SAEs will be provided.

13.2.2. Clinical Laboratory Evaluations

Descriptive statistics summarizing central laboratory data (hematology and chemistry) will be presented for all study visits. Changes from pretreatment to each study visit will also be summarized by treatment group.

13.2.3. Additional Safety Analysis

Additional safety assessments include vital signs and ECGs. Descriptive statistics of the vital sign and ECG parameters will be presented by treatment group and study visit, as well as the change from pretreatment at each visit.

13.2.4. Cardiovascular Adjudication Committee

In addition to potential clinical endpoint events, cardiovascular events will be adjudicated. The adjudication of these events will be handled separately from the adjudication of events for assessment of the primary endpoint in this study. Adjudicated cardiovascular events include core MACE (cardiovascular death, nonfatal myocardial infarction, and nonfatal stroke) and expanded MACE (unstable angina requiring hospitalization, transient ischemic attack, peripheral or coronary revascularization procedures, hospitalization for congestive heart failure). Other events potentially related to adverse cardiovascular outcomes may be included in the Cardiovascular Adjudication Committee (CAC) Charter for adjudication. The adjudication of these events will be handled separately from the adjudication of events for assessment of the primary endpoint in this study (see [Section 13.4](#)).

13.3. Data Monitoring Committee

An independent DMC that includes hepatologists, pharmaceutical physicians, epidemiology/cardiology expert(s), and statistician(s) not involved in the study as Investigators, adjudication committee members, or consultants. The DMC will have oversight over the study conduct as defined by the DMC charter. All members will have considerable experience with clinical study conduct and DMCs. Any candidate found to have a conflict of interest or whose name is listed on the FDA debarment list will not be offered membership. Conflicts of interest will be assessed regularly, and if members are found to have a new conflict of interest they will be replaced.

The DMC will meet approximately quarterly at scheduled meetings and ad hoc meetings will be convened, as appropriate, to review safety and efficacy data in order to ensure the safe and proper treatment of subjects. Based on review of these data, the DMC will advise the Sponsor on the validity and scientific merit of continuing the study.

Written minutes of both the open and closed DMC sessions will be prepared. The closed minutes will be made available to the appointed Sponsor representatives only after the database is locked.

Data listings provided to the DMC do not contain individual subject treatment information; however, the DMC will have access to the database and may unblind individual subject data as appropriate. Summary tables reviewed by the DMC during closed sessions will include an overall column containing information regarding all subjects and separate treatment columns with 'dummy' labels, ie, the actual treatment groups are used, but are not identified. Data reviewed during the meetings will include, at a minimum, disposition, demographics, exposure, clinical laboratory results, Medical Dictionary for Regulatory Activities (MedDRA) coded AEs, and AEs leading to early withdrawal of investigational product. At each meeting, detailed narratives of interval SAEs (including events resulting in death) are reviewed by the DMC in addition to a cumulative list of all SAEs.

The DMC may agree to adjust meeting frequency based upon actual and projected safety and efficacy data availability. Adjustments to or stopping of the protocol defined doses may be considered based on DMC evaluation of OCA safety and tolerability.

All Investigators and responsible IRBs/IECs will be informed of any decisions made by the Sponsor based on recommendations from the DMC relating to subject safety, which alter the conduct of this study. The Investigators will inform the subjects of such actions and the protocol, patient information sheet (PIS), and consent will be revised, as appropriate.

